5.3.5.10 Hospitalization or Prolonged Hospitalization

Any adverse event that results in hospitalization (i.e., inpatient admission to a hospital) or prolonged hospitalization should be documented and reported as a serious adverse event (per the definition of serious adverse event in Section 5.2.2), except as outlined below.

- Hospitalization for a preexisting condition, provided that the following criteria are met:

The hospitalization was planned prior to the study or was scheduled during the study when elective surgery became necessary because of the expected normal progression of the disease.

The patient has not experienced an adverse event.

5.3.5.11 Adverse Events Associated with an Overdose or Error in Drug Administration

An overdose is the accidental or intentional use of a drug in an amount higher than the dose being studied. An overdose or incorrect administration of study treatment is not itself an adverse event, but it may result in an adverse event.

Any study drug overdose or incorrect administration of study treatment should be noted on the study drug administration form (eCRF).

All adverse events associated with an overdose or incorrect administration of study drug should be recorded on the Adverse Event eCRF. If the associated adverse event fulfills seriousness criteria, the event should be reported to the Sponsor immediately (i.e., no more than 24 hours after learning of the event; see Section 5.4.2).

No safety data related to overdosing of RO6867461 are available.

5.4 IMMEDIATE REPORTING REQUIREMENTS FROM INVESTIGATOR TO SPONSOR

Certain events require immediate reporting to allow the Sponsor to take appropriate measures to address potential new risks in a clinical trial. The investigator must report such events to the Sponsor immediately; under no circumstances should reporting take place more than 24 hours after the investigator learns of the event. The following is a list of events that the investigator must report to the Sponsor within 24 hours after learning of the event, regardless of relationship to study drug:

- Serious adverse events (see Section 5.4.2 for further details)
- Adverse events of special interest (see Section 5.4.2 for further details)
- Pregnancies (see Section 5.4.3 for further details)

The investigator must report new significant follow-up information for these events to the Sponsor immediately (i.e., no more than 24 hours after becoming aware of the information). New significant information includes the following:

- New signs or symptoms or a change in the diagnosis
- Significant new diagnostic test results
- Change in causality based on new information
- Change in the event's outcome, including recovery
- Additional narrative information on the clinical course of the event

Investigators must also comply with local requirements for reporting serious adverse events to the local health authority and IRB/EC.

5.4.2 Reporting Requirements for Serious Adverse Events and Adverse Events of Special Interest

5.4.2.1 Events That Occur prior to Study Drug Initiation

After informed consent has been obtained but prior to initiation of study drug, only serious adverse events caused by a protocol-mandated intervention should be reported. The Serious Adverse Event/Adverse Event of Special Interest Reporting Form provided to investigators should be completed and submitted to the Sponsor or its designee immediately (i.e., no more than 24 hours after learning of the event), either by faxing or by scanning and emailing the form using the fax number or email address provided to investigators.

5.4.2.2 Events That Occur after Study Drug Initiation

After initiation of study drug, serious adverse events and adverse events of special interest will be reported until 28 days after the last dose of study drug. Investigators should record all case details that can be gathered immediately (i.e., within 24 hours after learning of the event) on the Adverse Event eCRF and submit the report via the electronic data capture (EDC) system. A report will be generated and sent to Roche Safety Risk Management by the EDC system.

In the event that the EDC system is unavailable, the Serious Adverse Event/Adverse Event of Special Interest Reporting Form provided to investigators should be completed and submitted to the Sponsor or its designee immediately (i.e., no more than 24 hours after learning of the event), either by faxing or by scanning and emailing the form using the fax number or email address provided to investigators. Once the EDC system is available, all information will need to be entered and submitted via the EDC system.

Instructions for reporting serious adverse events that occur >28 days after the last dose of study treatment are provided in Section 5.6.

5.4.3 Reporting Requirements for Pregnancies

5.4.3.1 Pregnancies in Female Patients

Female patients of childbearing potential will be instructed to immediately inform the investigator if they become pregnant during the study or within 28 days after the last dose of study drug. A Clinical Trial Pregnancy Reporting Form should be completed and submitted to the Sponsor or its designee immediately (i.e., no more than 24 hours after learning of the pregnancy), either by faxing or by scanning and emailing the form using the fax number or email address provided to investigators. Pregnancy should not be recorded on the Adverse Event eCRF. The investigator should counsel the patient, discussing the risks of the pregnancy and the possible effects on the fetus. Monitoring of the patient should continue until conclusion of the pregnancy. Any serious adverse events associated with the pregnancy (e.g., an event in the fetus, an event in the mother during or after the pregnancy, or a congenital anomaly/birth defect in the child) should be reported on the Adverse Event eCRF. In addition, the investigator will submit a Clinical Trial Pregnancy Reporting Form when updated information on the course and outcome of the pregnancy becomes available.

5.4.3.2 Abortions

Any abortion should be classified as a serious adverse event (as the Sponsor considers abortions to be medically significant), recorded on the Adverse Event eCRF, and reported to the Sponsor immediately (i.e., no more than 24 hours after learning of the event; see Section 5.4.2).

5.4.3.3 Congenital Anomalies/Birth Defects

Any congenital anomaly/birth defect in a child born to a female patient exposed to study drug should be classified as a serious adverse event, recorded on the Adverse Event eCRF, and reported to the Sponsor immediately (i.e., no more than 24 hours after learning of the event; see Section 5.4.2).

5.5 FOLLOW-UP OF PATIENTS AFTER ADVERSE EVENTS

5.5.1 Investigator Follow-Up

The investigator should follow each adverse event until the event has resolved to baseline grade or better, the event is assessed as stable by the investigator, the patient is lost to follow-up, or the patient withdraws consent. Every effort should be made to follow all serious adverse events considered to be related to study drug or trial-related procedures until a final outcome can be reported.

During the study period, resolution of adverse events (with dates) should be documented on the Adverse Event eCRF and in the patient's medical record to facilitate source data verification.

All pregnancies reported during the study should be followed until pregnancy outcome.

5.5.2 Sponsor Follow-Up

For serious adverse events, adverse events of special interest immediately reportable to the Sponsor, and pregnancies, the Sponsor or a designee may follow up by telephone, fax, electronic mail, and/or a monitoring visit to obtain additional case details and outcome information (e.g., from hospital discharge summaries, consultant reports, autopsy reports) in order to perform an independent medical assessment of the reported case.

5.6 ADVERSE EVENTS THAT OCCUR AFTER THE ADVERSE EVENT REPORTING PERIOD

The Sponsor should be notified if the investigator becomes aware of any serious adverse event that occurs after the end of the adverse event reporting period (defined as 28 days after the last dose of study treatment), if the event is believed to be related to prior study drug treatment. These events should be reported through use of the Adverse Event eCRF. However, if the EDC system is not available, the investigator should report these events directly to the Sponsor or its designee, either by faxing or by scanning and emailing the Serious Adverse Event/Adverse Event of Special Interest Reporting Form using the fax number or email address provided to investigators.

5.7 EXPEDITED REPORTING TO HEALTH AUTHORITIES, INVESTIGATORS, INSTITUTIONAL REVIEW BOARDS, AND ETHICS COMMITTEES

The Sponsor will promptly evaluate all serious adverse events and adverse events of special interest against cumulative product experience to identify and expeditiously communicate possible new safety findings to investigators, IRBs, ECs, and applicable health authorities based on applicable legislation.

To determine reporting requirements for single adverse event cases, the Sponsor will assess the expectedness of these events using the following reference documents:

- RO6867461 Investigator's Brochure
- Ranibizumab U.S. Prescribing Information

The Sponsor will compare the severity of each event and the cumulative event frequency reported for the study with the severity and frequency reported in the applicable reference document.

Reporting requirements will also be based on the investigator's assessment of causality and seriousness, with allowance for upgrading by the Sponsor as needed.

The IMC will monitor the incidence of these expected events during the study. An aggregate report of any clinically relevant imbalances that do not favor RO6867461 will be submitted to health authorities.

6. STATISTICAL CONSIDERATIONS AND ANALYSIS PLAN

6.1 DETERMINATION OF SAMPLE SIZE

The focus of this trial is estimation rather than hypothesis testing. The sample size was determined largely based on logistical considerations. Assuming a common standard deviation for BCVA change from baseline of 13.5 letters, the distance from the difference of the means between RO6867461 ($n=30$) and ranibizumab ($n=15$) to the 80% two-sided confidence interval bounds is estimated to be 5.5 letters.

6.2 SUMMARIES OF CONDUCT OF STUDY

The number of patients who are enrolled, discontinued, and completed the study will be summarized as well as the major protocol violations. Demographic and other baseline characteristics will be summarized with descriptive statistics.

6.3 SUMMARIES OF TREATMENT GROUP COMPARABILITY

Demographics, baseline characteristics (including ocular assessments, patient disposition, and medical history), and all baseline laboratory values will be summarized descriptively by treatment group using frequency tables and summary statistics providing means, medians, standard deviations, first and third quartiles, and extreme values.

6.4 EFFICACY ANALYSES

The primary, secondary, and exploratory efficacy analyses will be carried out in the intent-to-treat population (defined as all randomized patients), with patients grouped according to their assigned treatment.

The baseline measurement is defined as the latest non-missing observation before the first dose of study medication.

6.4.1 Primary Efficacy Endpoint

The primary efficacy endpoint is BCVA change from baseline at Week 40. The primary efficacy analysis will be performed using a Mixed Model for Repeated Measurement (MMRM) model. The model will include the categorical covariates of treatment group, visit, and visit by treatment group interaction and the continuous covariate of baseline BCVA. An unstructured covariance will be used to account for within-patient correlation, but another variance-covariance structure, such as AR(1), may be selected in case of convergence issues.

Means for RO6867461 and ranibizumab arms, difference of the means relative to ranibizumab, and the corresponding two-sided 80% confidence intervals will be computed. There will not be formal correction for multiple testing.

6.4.2 Secondary Efficacy Endpoints

Mean change from baseline BCVA over time using the ETDRS-like charts will be analyzed using the MMRM model described in Section 6.4.1.

Categorical outcomes measured repeatedly will be analyzed using Generalized Estimating Equations with a binomial distribution, logit link function, and unstructured covariance. In case of convergence issues, AR(1) covariance structure will be used. The model will include the categorical covariates of treatment group, visit, and visit by treatment group interaction. Least squares means with the corresponding two-sided 80% confidence intervals and odds ratios will be computed.

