The focus of this trial is estimation rather than hypothesis testing. The sample size was determined largely based on logistical considerations. Assuming a common standard deviation for BCVA change from baseline of 13.5 letters, the distance from the difference of the means between RO6867461 (n=30) and ranibizumab (n=15) to the 80% two-sided confidence interval bounds is estimated to be 5.5 letters.

Optional Interim Analyses

Given the hypothesis-generating nature of this study, the Sponsor may choose to conduct up to two interim efficacy analyses. The decision to conduct an optional interim analysis and the timing of the analysis will be documented in the Sponsor's trial master file prior to the conduct of the interim analysis. The interim analysis will be performed by the Sponsor IMC and appropriate senior management personnel who will be unmasked at the treatment group level. Access to treatment assignment information will follow the Sponsor's standard procedures.

LIST OF ABBREVIATIONS AND DEFINITIONS OF TERMS

Abbreviation	Definition
ADA	anti-drug antibody
ALP	alkaline phosphatase
ALT	alanine aminotransferase
AMD	age-related macular degeneration
Ang-1	angiopoietin-1
Ang-2	angiopoietin-2
aPTT	activated partial thromboplastin time
AST	aspartate aminotransferase
ATE	arterial thromboembolic event
AUC	area under the concentration–time curve
BCVA	best corrected visual acuity
BP	blood pressure
CFT	central foveal thickness
C _{max}	maximum concentration observed
CNV	choroidal neovascularization
CRO	contract research organization
CST	central subfield thickness
DLE	dose-limiting event
DMC	Data Monitoring Committee
DME	diabetic macular edema
EC	Ethics Committee
eCRF	electronic Case Report Form
EDC	electronic data capture
EDI	enhanced depth imaging
ETDRS	Early Treatment Diabetic Retinopathy Study
FDA	Food and Drug Administration
FFA	fundus fluorescein angiography
FP	fundus photography
GLP	Good Laboratory Practice
HIPAA	Health Insurance Portability and Accountability Act
HCT	hematocrit
ICH	International Council on Harmonisation
IgG1	immunoglobulin G1
IMC	Internal Monitoring Committee
IMP	investigational medicinal product

Abbreviation	Definition
IND	Investigational New Drug (application)
INR	international normalized ratio
IOP	intraocular pressure
IRB	Institutional Review Board
IVT	intravitreal(ly)
IxRS	Interactive Voice and Web Response System
LPLV	last patient, last visit
mAb	monoclonal antibody
MCH	mean corpuscular hemoglobin
MCV	mean corpuscular volume

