3. STUDY DESIGN

3.1 DESCRIPTION OF THE STUDY

3.1.1 Overview of the Study Design

This is a Phase II, multicenter, randomized, active comparator-controlled, subject and outcome-assessor masked, parallel group, 52-week study to investigate the efficacy, safety, and pharmacokinetics of RO6867461 administered at 12- and 16-week intervals in treatment-naive patients with nAMD. Approximately 75 patients will be enrolled and randomized in a 2:2:1 ratio to one of three treatment arms:

- Arm A (Q12W): 6 mg RO6867461 IVT every 4 weeks up to Week 12 (4 injections), followed by 6 mg RO6867461 IVT every 12 weeks up to Week 48 (injections at Weeks 24, 36, and 48; 3 injections)
- Arm B (Q16W): 6 mg RO6867461 IVT every 4 weeks up to Week 12 (4 injections), followed by 6 mg RO6867461 IVT every 16 weeks up to Week 48 (injections at Weeks 28 and 44; 2 injections)

A protocol-defined assessment of disease activity at Week 24 requires Arm B patients with active disease (see criteria below) to switch to a 12-weekly dosing regimen of 6 mg RO6867461 for the remainder of the study, with injections commencing at Week 24 and repeated at Weeks 36 and 48.

- Arm C (comparator arm): 0.5 mg ranibizumab IVT every 4 weeks for 48 weeks (13 injections)

Only one eye will be chosen as the study eye.

The total duration of the study for each patient will be up to 56 weeks, divided as follows:

- Screening: up to 4 weeks prior to or on the same day as randomization
- Randomization: Day 1
- Study Treatment Administration: from Day 1 to Week 48
- Final Visit: Week 52

Patients will undergo a screening examination within 4 weeks of study treatment administration. The screening and Week 1/Day 1 (randomization) visit may occur as a combined visit if all assessments (*with the exception of informed consent*) are completed within 48 hours. *Informed consent must be documented before any study-specific screening procedure is performed, and may be obtained more than 28 days before initiation of study treatment.* Where screening and randomization are combined, assessments listed for both visits only need to be conducted once. During screening (or the combined screening/Day 1 visit), the patient's eligibility will be assessed, including a central review of fundus photography (FP), spectral domain optical coherence tomography (SD-OCT), and fundus fluorescein angiography (FFA) to ensure that CNV secondary to AMD meets the predefined ocular criteria in the study.

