4.2 METHOD OF TREATMENT ASSIGNMENT AND MASKING

4.2.1 Treatment Assignment

After written informed consent has been obtained, all patients will receive a screening number assigned through the Interactive Voice and Web Response System (IxRS). A patient must satisfy all eligibility criteria (see Section 4.1.1 and Section 4.1.2) prior to randomization.

Patients will be randomized on the same day the study treatment is to be initiated (Day 1 visit). After randomization and at each visit with study treatment administration (i.e., including Day 1) the IxRS will assign the appropriate study treatment kit to be used.

Randomization will be stratified for baseline BCVA ETDRS letter score assessed on Day 1 (55 letters or better vs. 54 letters or worse).

Randomization with fixed permuted blocks will be used to obtain an approximate 2:2:1 ratio between the different arms within each stratum.

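### The GEE for 20/40-or-better and 20/200-or-worse leaves out baseline BCVA, so the chance baseline imbalance that remains after stratification enters those two comparisons unadjusted

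*Combined protocol and SAP*

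**What the plan says.** Section 6.4.2 analyses repeated categorical outcomes by GEE with a binomial distribution, logit link and unstructured covariance, falling back to AR(1) if the fit does not converge. Its list of terms is complete in one sentence: "The model will include the categorical covariates of treatment group, visit, and visit by treatment group interaction". Least squares means with two-sided 80% intervals, and odds ratios, are to be reported.

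The MMRM in Section 6.4.1 has the same terms and one more: "visit by treatment group interaction and the continuous covariate of baseline BCVA". Section 6.4.2 reuses that model for mean BCVA change over time.

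Section 4.2.1 stratifies randomisation on the Day 1 letter score, cut between 54 and 55, and adds: "Randomization with fixed permuted blocks will be used to obtain an approximate 2:2:1 ratio between the different arms within each stratum". The block size is not given.

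Section 2 (Table 1) lists ten categorical BCVA endpoints: four gain thresholds, four avoid-loss thresholds, 20/40 or better, and 20/200 or worse. No other section adds a baseline term to this GEE. The baseline covariates in Section 6.5 belong to a separate drug-disease model.

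**The concern.** The plan treats baseline acuity as important enough to stratify on and to adjust for in the primary model, then drops it without explanation for binary outcomes built from the same letter score. The omission bears on the two absolute-level endpoints. Section 4.1.1 admits 24 to 73 letters, which it equates to 20/320 to 20/40. Both thresholds therefore lie within the entry range, and some patients may meet one of these endpoints on Day 1, before treatment. A single cut at 54/55 leaves wide variation within strata (24 to 54 and 55 to 73).

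As written, mean BCVA change at a visit is baseline-adjusted and the proportion at 20/40 or better at that visit is not. If the two pointed in different directions, part of the discrepancy could be baseline imbalance. Section 6.3 would display that imbalance, but the plan has no prespecified analysis that accounts for it in the categorical comparison.

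**Working it through.** **Inputs from the documents.** Size and ratio (Section 3.1.1): "Approximately 75 patients will be enrolled and randomized in a 2:2:1 ratio to one of three treatment arms", so 30, 30 and 15. Spread (Section 6.1): "Assuming a common standard deviation for BCVA change from baseline of 13.5 letters". Entry range 24 to 73 letters (Section 4.1.1), strata cut at 54/55 (Section 4.2.1), two-sided 80% intervals (Section 6.4.2).

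**Assumptions not in the documents.** Baseline BCVA is either normal with mean 57 and SD 11 or 13, truncated to 24–73, or uniform on 24–73. Mean gain is 8 letters. The dependence of change on baseline is 0, −0.2 or −0.35. 20/40 or better means at least 69 letters. Block size is 5. There is no treatment effect.

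**1. The plan's own figure.** SE = 13.5 × √(1/30 + 1/15) = 13.5 × 0.3162 = 4.269. The 80% half-width is 1.2816 × 4.269 = 5.47 letters (5.56 with t on 43 df, 5.52 with t on 72 df). The stated 5.5 is reproduced. The plan gives no precision for categorical endpoints.

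**2. Baseline imbalance, Arm A minus Arm C.** Without stratification its SD is roughly σ_b × 0.3162. Simulation (5,000 trials per scenario) gives:

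| Baseline | σ_b | SD by formula | SD simulated, unstratified | SD simulated, stratified | P(≥3 letters), stratified |
|---|---|---|---|---|---|
| normal, 11 | 9.57 | 3.03 | 2.98 | 1.81 | 10% |
| normal, 13 | 10.65 | 3.37 | 3.34 | 1.97 | 13% |
| uniform | 14.45 | 4.57 | 4.54 | 2.52 | 24% |

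Stratified blocks remove about 40–45% of the SD (for example 1 − 1.81/2.98 = 39%; 1 − 2.52/4.54 = 44%).

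**3. Effect on the unadjusted difference.** Let a patient with baseline b have P(20/40 or better) = Φ[(b + 8 + β(b − μ) − 68.5)/r], with r = √(13.5² − β²σ_b²). Under stratified randomisation, normal baseline with SD 11, one visit:

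| β | Points per letter | Imbalance-driven SD | Total SD | 80% coverage |
|---|---|---|---|---|
| 0 | 2.1 | 4.0 | 14.4 | 81% |
| −0.2 | 1.8 | 3.4 | 14.6 | 80% |
| −0.35 | 1.6 | 2.9 | 14.5 | 80% |

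The mean error is within 0.3 points of zero throughout. For gain of at least 15 letters, each letter moves the difference by 0 to −0.9 points, the imbalance-driven SD is 0 to 1.7 points, and its share of the variance is 0–1%. A separate check (2,000 trials per scenario) put the 20/40 shift at 1.0–1.8 points per letter unadjusted and about 0 after adjustment. Together these give about 1 to 2 points per letter.

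**4. Precision to be gained.** If adjustment removed all the imbalance-driven variance, the SD ratio would be √(1 − 4.0²/14.4²) = 0.961, √(1 − 3.4²/14.6²) = 0.973 and √(1 − 2.9²/14.5²) = 0.980. Direct simulation of adjusted SD over unadjusted SD (1,500 trials per scenario; correlation of change with baseline 0, −0.2, −0.35) gave 0.965, 0.980, 0.993 (normal) and 0.959, 0.967, 0.983 (uniform). The separate check gave a fall of about 0–4%.

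**5. Intervals after adjustment.** With a plain sandwich variance, nominal 80% intervals for the standardised difference covered 74–79%, against 79–85% unadjusted. A leverage-corrected sandwich restored about 80%.

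All of this is at a single visit. The planned multi-visit GEE with unstructured covariance was not fitted.

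**The case against.** The strongest reply is that little is lost. Blocks within BCVA strata already remove much of the imbalance, and what remains is 4–8% of the variance of the 20/40 difference (4.0²/14.4² = 8%; 2.9²/14.5² = 4%). An imbalance-driven SD of 3 to 4 points sits inside an 80% half-width of about 18 to 19 points (1.28 × 14.4 to 14.6). The trial is for estimation, these endpoints are secondary, and mean BCVA is adjusted already. With 15 ranibizumab patients, adjustment can damage coverage or convergence and changes what the odds ratio means. All of this stands. It limits the priority and shapes the remedy, but it does not explain why a covariate already collected and used in the MMRM is left out.

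Four stronger readings should be resisted.

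- **Bias.** A reader might infer that the estimates are biased. They are not: error averages to about zero over randomisations. The shift applies only given the imbalance that occurs.
- **Every categorical BCVA endpoint.** For the eight gain and avoid-loss thresholds the effect is negligible.
- **A precision gain of 5–8%.** That figure divides the adjusted estimator's SD by the unadjusted reported SE (0.92 to 0.95 at correlations of 0 to −0.2, and 1.01 at −0.35). It is not like for like. Most of it reflects an unadjusted SE that is conservative under stratification.
- **The missing stratum factor as a separate fault.** The MMRM omits it too, and continuous baseline BCVA carries the information from which the stratum is derived.

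**Conclusion.** The omission is real and worth correcting for 20/40 or better and 20/200 or worse. Under the assumptions above, residual Arm A versus Arm C imbalance has an SD of about 2 to 2.5 letters. It moves the unadjusted 20/40-or-better difference by about 1 to 2 points per letter, so an imbalance of 3 letters (probability of that or more, 10–24%) means about 3 to 6 points. Adjustment takes this to about zero and lowers the true SD by about 0–4%. The benefit is mainly that the categorical and mean BCVA results rest on the same footing, with only a slight gain in precision.

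The sizes depend on the assumed baseline distribution, mean gain and dependence of change on baseline, none of which the documents give. For 20/200 or worse no like-for-like figure was derived; by the more generous measure (adjusted SD over unadjusted reported SE) the gain was at most about 5%.

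**What to change.** In Section 6.4.2:

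- Add continuous baseline BCVA, as in Section 6.4.1, to the GEE for 20/40 or better and 20/200 or worse only.
- Report standardised (marginal) proportions by arm, and their differences from ranibizumab, with two-sided 80% intervals based on a named small-sample-corrected sandwich variance.
- State a fixed fallback to the current unadjusted model if the adjusted model does not converge or an arm has no events, and say how this step is ordered relative to the existing AR(1) fallback.

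Leave the gain and avoid-loss models as they are.

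The cost is a few sentences of analysis text and some programming for the standardisation and corrected variance. No new data are needed. The model odds ratio for these two endpoints becomes conditional on baseline, which is why the standardised proportions should accompany it. The variance correction is needed because plain sandwich intervals under-cover with only 15 ranibizumab patients.
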